### 1.2.1 Primary Outcome

The primary outcome is part of the data collection DC1 and is defined as rate of hospitalizations (long-term care only) per 100 residents per year during the 12-months observation period, compared between intervention group and control group at t2. The rate of hospitalizations per 100 residents per year is defined as the quotient of the number of all hospitalizations in the last 12 months observation period divided by the number of occupied bed days multiplied by 365 (days) and 100 (residents).

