### 1.2.2 Secondary Outcomes

The secondary outcomes are as follows, analyzed at t2:

At NH level (DC1):

- 1. number of hospital days (long-term) per 100 residents per past 12 months
- 2. number of hospital stays (long-term) per 100 residents during observation period (without consideration of occupied bed days)
- 3. number of patients with at least one hospitalization per 100 residents per past 12 months
- 4. number of residents who died in the hospital per 100 residents per past 12 months
- 5. number of pre-specified unwanted invasive treatments per 100 residents measured:
  - a. number of residents with feeding tube (PEG) in place (cross-sectional)
  - b. number of residents with PEG in use (cross-sectional)
  - c. number of attempts of cardiopulmonary resuscitation (CPR) per past 12 months
  - d. number of attempts of successful CPR per past 12 months
- 6. number of legal guardians per 100 residents (cross-sectional)
- 7. number of durable powers of attorney (DPOA) per 100 residents (cross-sectional)
- 8. advance directives (ADs)
  - a. number of all advance directives per 100 residents (cross-sectional)
  - b. number of advance directives signed by resident per 100 ADs (cross-sectional)
  - c. number of advance directives last signed in the last 6m per 100 ADs (cross-sectional)
  - d. number of advance directives in long-term care only per 100 ADs (cross-sectional)

- 9. physician or patient/proxy orders for life sustaining treatment in emergencies (POLST-E)
  - a. number of POLST-E per 100 residents (cross-sectional)
  - b. number of POLST-E not signed by resident per 100 POLST-E (cross-sectional)
  - c. number of POLST-E in the last 6m per 100 POLST-E (cross-sectional)
  - d. number of POLST-E with a do-not-hospitalize order per 100 POLST-E (cross-sectional)
  - e. number of POLST-E per 100 residents (long-term care only; cross-sectional)

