## 2.7 Timing of outcome assessments

The timeline of the BEVOR study is as follows (see Fig. 2 of the study protocol): at the start of the study, data collection is initiated, which corresponds with the baseline measurement (t0). At the end of the run-in phase of the intervention, the 12-month observation phase begins (t1). The end of the observation phase corresponds with the measurement at 12-months follow-up (t2). The run-in phase of the intervention describes the time in which the intervention is established and reaches the residents, the NHs and the regions. It lasts from the time of randomization until t1. The intervention itself continues during the observation period.

The 12 months observation period's data will be collected in one follow up collection (DC1) or, respectively, for DC2 continuously over the entire period, including

- interviews with relatives and nursing home staff of deceased residents,
- four three-monthly sessions to identify all potentially life-threatening events and related treatment decisions for the respective preceding 3 months (3CP data collection including interviews), as appropriate.

The start of the observation phase (t1) is fixed for all study centres at 01.09.2021.

**NH level (DC1):** All outcomes on NH level will be measured at t0, t1 and t2 for the preceding 12 months.

**Resident's level (DC2):** Data collection 2 is performed with residents, their surrogates and/or relatives, and the respective nursing staff and contains three different sections with different time points:

- 1. Framework survey including quality of care survey is conducted at t0 and t2 for the 12 months observation period.
- 2. Care consistency with care preferences (3CP) is assessed at t0 for the preceding 3 months and at t2. Data collection at t2 will be splitted into 4 phases of the 12-months observation period (each covering the preceding 3 months), beginning 3 months after t1, to collect data over the twelve months of observation as accurately as possible. It is ensured that there is no overlap in the survey periods.
- 3. The survey of relatives and staff regarding deceased residents is conducted at t0 and continuously over the 12 months before t2.

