### 5.1.2 Primary Outcome

The primary analysis is performed in the ITT population at NH level. For rate comparison a Poisson regression model is calculated taking into account group (intervention vs control) as independent variable, realized follow-up time as offset, region of NHs and the respective baseline hospitalization rate as covariates. The treatment effect is presented as incidence rate ratio (IRR) with corresponding 95%-Confidence interval (CI) and p-value. Marginal estimators (numbers per 100 residents per past 12 -months observation period (from t1 to t2)) with corresponding 95%-CI are given per treatment group.

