### At NH level:

All secondary endpoints are count data.

For the endpoints 1,2, 4 and 5 c. & d., a Poisson Regression model is calculated with the respective number per 100 residents per past 12 months' observation period (from t1 to t2) as dependent variable, group (intervention vs control) as independent variable, number of occupied bed days as offset and the respective baseline rate and region of NHs as covariates.

The treatment effect is presented as incidence rate ratio (IRR) with corresponding 95%-CI and p-value. Marginal estimators (numbers per 100 residents per past 12 -months observation period (from t1 to t2)) with corresponding 95%-CI are given per treatment group.

For the secondary endpoint 3, the number of residents during the observation period before t2 is used as offset variable. The resulting marginal estimators are numbers per 100 residents.

The secondary endpoints 5 a. & b. and 6-7, 8 a. and 9 a. are measured cross-sectional. For these endpoints, a Poisson Regression model is calculated with the respective number as dependent variable, group (intervention vs. control) as independent variable, number of residents as offset and the respective baseline rate and region of NHs as covariates.

The treatment effect is presented as IRR with corresponding 95%-CI and p-value. Marginal estimators (numbers per 100 residents per past 12 -months observation period (from t1 to t2)) with corresponding 95%-CI are given per treatment group.

The secondary endpoints 8 b. - d. and 9 b. - e. are measured cross-sectional, too, but refer to a predefined subgroup.

For these endpoints, a Poisson Regression model is calculated with the respective number as dependent variable, group (intervention vs control) as independent variable and the respective baseline rate and region of NHs as covariates.

For the endpoints 8 b. - d. the number of ADs and for the endpoints 9 b. - e. the number of POLST-Es are set as offset, respectively.

The treatment effect is presented as IRR with corresponding 95%-CI and p-value. Marginal estimators (number per 100 ADs or 100 POLST-Es per past 12 -months observation period (from t1 to t2)) with corresponding 95%-CI are given per treatment group.

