### 5.4.2 Covid-19-Analysis

To assess the effect of the Covid-19 pandemic on the primary outcome, the following analysis is planned:

A mixed Poisson regression model is calculated taking into account group (intervention vs. control), time (t0, t1, t2) as well as the interaction between group and time as fixed effect, realized follow-up time as offset, the respective baseline hospitalization rate as covariate, and region of NHs and the respective NH as random intercept. The aim is to evaluate the effect of Covid-19 as external confounder on the primary outcome over time.

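### Secondary endpoint 2 is defined without occupied bed days but modelled with them as offset, so the defined quantity is not estimated

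*SAP*

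**What the plan says.** Section 1.2.2 defines endpoint 2 as "number of hospital stays (long-term) per 100 residents during observation period (without consideration of occupied bed days".

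Section 5.1.3 (At NH level) groups it with endpoints 1, 4, 5c and 5d. All five get a Poisson regression "with the respective number per 100 residents per past 12 months' observation period (from t1 to t2) as dependent variable", with "number of occupied bed days as offset and the respective baseline rate and region of NHs as covariates". The next endpoint in the same section is treated differently: "For the secondary endpoint 3, the number of residents during the observation period before t2 is used as offset variable".

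For the primary outcome, section 1.2.1 takes the number of long-term hospitalizations "divided by the number of occupied bed days multiplied by 365 (days) and 100 (residents". The primary model in 5.1.2 lists "realized follow-up time as offset, region of NHs and the respective baseline hospitalization rate as covariates", and the Covid-19 model in 5.4.2 likewise has "realized follow-up time as offset, the respective baseline hospitalization rate as covariate".

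**The concern.** The definition and the model of endpoint 2 name opposite denominators. The definition excludes bed days; the model divides by them. Nothing else in the SAP says which of the two governs.

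The denominator is the only visible feature that separates endpoint 2 from the primary outcome. Once bed days are the offset, that difference is gone. A table would then carry a second line labelled per 100 residents that in substance repeats the primary rate per bed day, and a reader could take the agreement of the two lines as support from a separate endpoint. The stays-per-resident view that the definition asks for would not be reported at all.

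**Working it through.** **1. Definitions and models side by side**

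| Outcome | Denominator in the definition | Offset in the model |
|---|---|---|
| Primary (1.2.1, 5.1.2) | occupied bed days | realized follow-up time |
| Endpoint 2 (1.2.2, 5.1.3) | residents, bed days excluded | occupied bed days |
| Endpoint 3 (1.2.2, 5.1.3) | residents | residents in the observation period |

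Endpoint 3 shows that a resident-based offset was available to the authors and was used where the definition called for it. Endpoint 2 is the row in which definition and model conflict outright.

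**2. What the endpoint 2 model estimates**

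Let Y be the count of stays in a home and B its bed days. With the raw count as outcome:

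log E(Y) = intercept + group + baseline rate + region + log(B).

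The group coefficient therefore compares Y/B between arms. The primary rate in 1.2.1 is Y/B × 365 × 100 = Y/B × 36,500. Since log(B/36,500) = log(B) − log(36,500), the scaling only shifts the intercept. The rate ratio, its confidence interval and its p-value are the same for both.

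One illustrative data set confirms this. The 44 homes and 8 regions are from SAP 2.1. Bed numbers, about 0.6 stays per resident-year, the true effect and somewhat higher turnover in the intervention arm are assumed. Every fit used the same baseline covariate.

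- Primary rate as defined (bed days/36,500): 0.8594 (0.7878 to 0.9375)
- Endpoint 2 as modelled (bed days): 0.8594 (0.7878 to 0.9375)
- Endpoint 2 as defined (residents): 0.8545 (0.7828 to 0.9327)

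The values depend on the invented data. The equality of the first two lines does not.

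**3. Size of the difference in level**

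The SAP gives neither a hospitalization rate nor a turnover figure, so both are assumed: 60 stays per 100 resident-years, and t new residents per place per year with places kept occupied. Each resident-year then corresponds to 1 + t persons, and stays per 100 persons = 60/(1 + t):

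- t = 0.3: 60/1.3 = 46.2
- t = 0.4: 60/1.4 = 42.9
- t = 0.5: 60/1.5 = 40.0

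The model as written would report 60. This takes residents to mean everyone who lived in the home during the 12 months. A head count on a single day would lie closer to the bed-day figure.

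**4. Size of the difference in the rate ratio**

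If turnover is t in the control arm and t + d in the intervention arm, the ratio per resident equals the ratio per bed day times (1 + t)/(1 + t + d). For t from 0.3 to 0.5:

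- d = 0: 1.000
- d = 0.02: 1.3/1.32 = 0.985 to 1.5/1.52 = 0.987
- d = 0.05: 1.3/1.35 = 0.963 to 1.5/1.55 = 0.968
- d = 0.10: 1.3/1.40 = 0.929 to 1.5/1.60 = 0.938

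The shift is nil with equal turnover, and about 1.3% to 7.1% over the assumed differences.

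**The case against.** The contradiction between 1.2.2 and 5.1.3 stands, but several things that a reader might build on it do not.

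**That endpoint 2 reproduces the primary result exactly.** This needs the raw count as outcome, hospital stays and hospitalizations to be the same events, the same baseline covariate, and bed days as the primary offset. The baseline rate for endpoint 2 could be its own, without bed days. Taken literally, 5.1.3 even makes a number already scaled per 100 residents the dependent variable and adds an offset, which would divide by exposure twice (0.8371 in the illustrative data). That is probably not meant: the section opens by calling all its endpoints counts, and per 100 residents reads naturally as the reporting scale. Near-duplicate is the supportable word.

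**That the primary model is mis-specified.** Realized follow-up time is not defined for a home, and section 2.7 says "All outcomes on NH level will be measured at t0, t1 and t2 for the preceding 12 months". Read as calendar time, the offset would be constant and the model would compare counts per home. The SAP does not support that reading. Section 1.2.1 fixes the exposure as bed days; 5.1.2 announces a comparison of rates, adjusts for a baseline rate and reports per 100 residents; and the resident-level part of 5.1.3 uses the same term for residents' exposure. Under the likely reading the primary result does not change.

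**That bed days wrongly include respite care.** Section 1.2 makes both care groups the default only where nothing else is stated. The primary rate and endpoints 1 and 2 carry a long-term label, so a matching denominator is the ordinary reading.

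What also stands is proportion: endpoint 2 is exploratory under 5.1.3 and is not among the key secondary endpoints in 1.2.2.

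**Conclusion.** The endpoint 2 contradiction is certain from the text and should be corrected; its consequences are limited. As written, the plan estimates a rate per bed day where it defines stays per resident, and the result would be close to a repeat of the primary outcome. No primary or key secondary conclusion changes.

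The reported level would be 60 instead of roughly 46 to 40 per 100 residents. The treatment effect moves only with a turnover difference between arms, and by single-digit percentages over the range tried. The stay rate, the turnover and the turnover differences are all assumptions. The mismatch itself rests on none of them.

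The loose name for the exposure in 5.1.2 and 5.4.2 is a wording gap with no expected effect on any result. It is not evidence of an error in the primary analysis.

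**What to change.** In 5.1.3, take endpoint 2 out of the bed-day group. Model the raw count of long-term stays with the log of the number of long-term residents over t1 to t2 as offset, in the way endpoint 3 already uses residents.

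First check that this number exists. Section 4.5 lists resident numbers with a note on respite and long-term care, but for t0 and t1, and the note may describe a combined total. Endpoint 3 needs resident numbers for the observation period but is not labelled long-term. If long-term numbers are not recorded separately for t1 to t2, either change the definition in 1.2.2 to match the model or drop the endpoint as redundant.

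Minor wording at the same time: in 5.1.2 and 5.4.2 name the offset as log(occupied bed days) of the matching 12-month period, in line with 1.2.1; in 5.1.3 state that the dependent variable for endpoints 1, 2, 4, 5c and 5d is the raw count.

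The cost is one changed line for endpoint 2, a few words in three sections and one data check. The choice of denominator should be on record before unblinding, which section 1 places after finalization of the SAP.

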### 1.2 Objectives

The goal of the multicenter BEVOR study is to evaluate the effectiveness of a structured advance care planning (ACP) program in NH residents regarding the reduction of unwanted medical interventions, notably hospital admissions, as compared to a control group. Conversely, the rate of residents whose treatment preferences are known and honored should be increased.

In the following, the time point of baseline measurement is defined as t0, of the end of the run-in phase of the intervention as t1, and of succeeding 12-months follow-up as t2. For more details, see section 2.7.

Researchers will take two independent approaches for data collection:

Firstly, participating NHs will provide anonymous pooled data on all their residents which include long-term as well as respite care residents of a defined time period (data collection 1 = DC1), including the hospitalization rate (primary outcome).

If not stated otherwise, data of both groups are used, long-term and respite care residents.

Secondly, a cohort of all long-term residents who have given informed consent (or for whom their health care proxy has given informed consent), their health care proxies and/or relatives, and the

respective nursing staff will be repeatedly surveyed until t2 (or until residents die earlier) (data collection 2 = DC2).

The following primary hypothesis will be tested:

**Primary hypothesis:** Compared to the control group, the structured ACP program reduces the 12-month hospitalization rate of residents of NHs at t2.

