- 25. number of EMS transports per 100 residents per last 12 months at t2
- 26. number of general practitioner visits per 100 residents per last 12 months at t2
- 27. number of referrals to specialists per 100 residents per last 12 months at t2
- 28. proportion of residents who received at least 1 antibiotic at t2
- 29. proportion of residents with legal guardian at t2
- 30. quality of life: residents capable of self-rating use WHO-QoL German Version; residents incapable of self-rating use QUALIDEM at t2
- 31. Process parameters measuring the effect of ACP at t2:
  - a. proportion of residents with advance care plans signed by facilitators, and/or physicians and/or representatives
  - b. proportion of residents with durable power of attorney
  - c. proportion of residents with POLST-E
  - d. proportion of residents with any ADs

BEVOR // UKE 2023

- e. proportion of ADs signed by resident
- f. proportion of residents with AD-by proxy
- g. proportion of residents with POLST-E
- 32. Anxiety, depression and trauma among bereaved relatives at t2:
  - a. Scoring on Revised Impact of Event Scale (IES-R): min. 0 pts, max. 88 pts., higher score indicates higher impact (trauma)
  - b. Scoring in German version of Hospital Anxiety and Depression Score (HADS-D): min. 0, max. 14, higher score indicates higher degrees of anxiety and depression

Key secondary endpoints are 9e, 10a ii and 10b ii. This choice is informed by blinded baseline analyses.

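### Key secondary endpoint 9e is defined per 100 long-term residents but modelled per POLST-E, so its analysis cannot show a change in POLST-E prevalence

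*SAP*

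**What the plan says.** Section 1.2.2 of the SAP lists five POLST-E endpoints at nursing-home level. Endpoint 9e is "number of POLST-E per 100 residents (long-term care only; cross-sectional", so its denominator is residents. Endpoints 9b to 9d have POLST-Es as denominator; 9d, for instance, is "number of POLST-E with a do-not-hospitalize order per 100 POLST-E (cross-sectional". The same section gives 9e special standing: "Key secondary endpoints are 9e, 10a ii and 10b ii".

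Section 5.1.3 (At NH level) then assigns the models. Endpoint 9a, the same measure as 9e but in all residents, is put with the cross-sectional endpoints that have "number of residents as offset and the respective baseline rate and region of NHs as covariates". Endpoint 9e is put elsewhere: "The secondary endpoints 8 b. - d. and 9 b. - e. are measured cross-sectional, too, but refer to a predefined subgroup". For this second group the SAP states "for the endpoints 9 b. - e. the number of POLST-Es are set as offset, respectively", and the results are to be given as "Marginal estimators (number per 100 ADs or 100 POLST-Es per past 12 -months observation period (from t1 to t2".

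On the population, section 1.2 says "If not stated otherwise, data of both groups are used, long-term and respite care residents".

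**The concern.** The definition and the model for 9e use different denominators. Section 1.2.2 asks how common POLST-Es are among long-term residents. The model in section 5.1.3 asks what fraction of the existing POLST-Es belongs to long-term residents. A programme that multiplies POLST-Es in a home raises the count and the offset together, and the effect cancels.

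This matters because 9e is one of only three endpoints singled out as key. Sections 5.2 and 5.4.1 carry the key secondary endpoints into the per-protocol, adherence and subgroup analyses, and those reuse the same model. Followed literally, the SAP would report a rate ratio near 1 for 9e in each of them, even after a large rise in POLST-E use. A reader would take that for absence of effect.

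**Working it through.** The SAP states no figure on this point, so there is none to reproduce. The check is algebra, followed by an illustration with assumed prevalences.

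**Inputs from the SAP.** Definition and key status of 9e (section 1.2.2); offset and reporting scale for 9b to 9e and for 9a (section 5.1.3); 44 homes, 22 per group, about 100 residents each (section 2.3).

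**Inputs assumed.** POLST-E prevalence in long-term residents: control p_C of 10% to 30%, intervention p_I of 20% to 60%. Respite share r of residents: 0%, 4% and 10%. None of these is in the SAP.

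**Step 1: what the model estimates.** In a Poisson model with log(offset), the exponentiated group coefficient is the ratio between arms of expected count divided by offset.

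- Offset = long-term residents: ratio = p_I / p_C, the prevalence ratio. This is the endpoint as defined.
- Offset = all POLST-Es in the home: ratio = s_I / s_C, where s is the share of POLST-Es held by long-term residents.
- Offset = POLST-Es of long-term residents only: count equals offset in every home, so the ratio is exactly 1.

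**Step 2: how far s_I / s_C can move.** Write R = p_I / p_C.

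- If there are no respite residents, or their prevalence rises by the same factor R, then s_I = s_C and the ratio is 1.
- If only long-term residents respond, and both resident types have the same prevalence in the control arm, then s_C = 1 − r and s_I = (1 − r)R / [(1 − r)R + r]. Hence s_I / s_C = R / [(1 − r)R + r].

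| Assumed prevalence, control vs intervention | Prevalence ratio R | SAP offset, r = 4% | SAP offset, r = 10% |
|---|---|---|---|
| 10% vs 20%, or 30% vs 60% | 2.0 | 2 / 1.96 = 1.02 | 2 / 1.90 = 1.05 |
| 20% vs 50% | 2.5 | 2.5 / 2.44 = 1.02 | 2.5 / 2.35 = 1.06 |
| 10% vs 40% | 4.0 | 4 / 3.88 = 1.03 | 4 / 3.70 = 1.08 |

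As R grows without limit the ratio tends to 1 / (1 − r): 1 / 0.96 = 1.04 and 1 / 0.90 = 1.11.

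**Step 3: simulation check.** Poisson models were fitted to 22 versus 22 homes of 100 residents, with 300 replicates per scenario. Region, baseline rate and between-home variation were left out.

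- With long-term residents as offset, the mean rate ratios were 2.0, 4.0, 2.5 and 2.0 for 10% vs 20%, 10% vs 40%, 20% vs 50% and 30% vs 60%. P was below 0.05 in every replicate.
- With the SAP's offset, the mean was about 1.00 when respite residents responded alike or were absent, with no replicate below 0.05.
- With the SAP's offset and only long-term residents responding, the means were 1.02 to 1.03 (4% respite) and 1.05 to 1.08 (10% respite), as in the table. At most 0.3% of replicates had p below 0.05.

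The detection rate of 100% with the resident offset is flattered by leaving out between-home variation. The contrast between the two offsets follows from the algebra alone.

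**The case against.** Four points can be made for the plan.

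*The definition, not the model, may be the slip.* Endpoint 8d counts advance directives in long-term care per 100 advance directives, and section 5.1.3 groups 8b to 8d with 9b to 9e consistently. Endpoint 9e could have been meant as the counterpart of 8d. But 8d states its denominator as advance directives, while 9e states residents, and the long-term share of POLST-Es says nothing about whether the programme increases them. That is an unlikely choice for a key endpoint. What stands is that the sponsor should confirm the intended quantity; the two sections cannot both be right.

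*The harm is limited.* Secondary outcomes are exploratory and not adjusted for multiplicity, the primary outcome is untouched, and POLST-E prevalence is still estimated by 9a and by the resident-level outcomes 31c and 31g. This is correct and confines the defect to 9e and the analyses built on it. It does not repair 9e.

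*It is only a letter-range error.* Quite possibly the range should end at d. But the grouping, the offset and the reporting scale all include 9e. An analyst following the text would run the wrong model, and a correction made after unblinding would be a late change to a key endpoint.

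*Homes with no POLST-E.* Such homes have log(0) as offset and would drop out, but no weight should be put on this. The SAP does not say how many there are or in which arm. At 10% prevalence and the average of 96 residents in section 2.1, the chance of none is 0.9^96, about 0.00004 per home; at 2% it is 0.98^96, about 0.14. The issue would also affect 9b to 9d, where POLST-Es are the right denominator.

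**Conclusion.** The concern holds. For 9e, sections 1.2.2 and 5.1.3 contradict each other, and no other part of the SAP gives 9e a different model. As written, the analysis estimates the long-term share of POLST-Es, which carries little or no information on prevalence. That conclusion needs no assumed figure.

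The size does rest on assumptions: a true prevalence ratio of 2 to 4 would appear as 1.00 to 1.08 for respite shares up to 10% and equal control-arm prevalence in both resident types. Any departure from 1 would reflect differences between long-term and respite residents, not the spread of POLST-Es as such. Because 9e is a key secondary endpoint, this must be corrected before the analysis.

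**What to change.** In section 5.1.3:

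- Confine the POLST-E offset, and the group it belongs to, to 9b to 9d.
- Move 9e to the group of 9a, with the number of long-term residents on the day of data collection as offset.
- Compute the baseline-rate covariate for 9e on the same denominator.
- Report its marginal estimates per 100 long-term residents. Since 9e is cross-sectional, they should not be expressed over a 12-month period.
- State that the per-protocol, adherence and subgroup analyses of 9e use this model.

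If the sponsor did intend the share of POLST-Es, section 1.2.2 must be changed instead, and its place among the key endpoints justified.

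The cost is a few sentences of SAP wording. Section 4.5 lists resident numbers on the day of data collection for respite and long-term care, but for t0 and t1. The sponsor should confirm that the long-term count is also available at t2, which the definition of 9e already requires. The change should be dated and made before the analysts learn the allocation.
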